7.1.2.8 Laboratory Procedures/Assessments

The total amount of blood/tissue to be drawn/collected over the course of the trial (from pre-trial to post-trial visits), including approximate blood/tissue volumes drawn/collected by visit and by sample type per subject can be found in Table 8.

Table 8 Volume of blood to be drawn from each subject

Assessment		Sample volume (mL)	No. of samples	Total volume (mL)
Safety	Clinical chemistry	4	4	16
	Hematology	4	4	16
Pharmacodynamic	PBMC	40	5	200
	⁸⁹ Zr-pembrolizumab PET	7	2	14
Total				246

7.1.2.9 Laboratory Safety Evaluations (Hematology, Chemistry and Urinalysis)

Laboratory tests for hematology, chemistry, urinalysis, and others are specified in Table 9. Laboratory tests for screening should be performed within 10 days prior to the first dose of treatment. After Cycle 1, pre-dose laboratory procedures can be conducted up to 72 hours prior to dosing. Results must be reviewed by the investigator or qualified designee and found to be acceptable prior to each dose of trial treatment.

Table 9 Laboratory Tests

Hematology	Chemistry	Other
Hematocrit	Albumin	Free thyroxine (T4)
Hemoglobin	Alkaline phosphatase	Thyroid stimulating hormone (TSH)
Platelet count	Alanine aminotransferase (ALT)	
Total WBC	Aspartate aminotransferase (AST)	Blood for correlative studies
	Lactate dehydrogenase (LDH)	
	Creatinine	
	Calcium	
	Glucose	
	Phosphorus	
	Potassium	
	Sodium	
	Magnesium	
	Total Bilirubin	

7.1.2.10 Immunophenotyping on peripheral blood

To evaluate the pre- and on-treatment immune status, polychromatic flowcytometric analyses of lymphoid and myeloid subsets in peripheral blood will be performed at t = 0, 21 days (immediately prior to 2nd therapeutic dose), just before surgery, one week after surgery and after 6 months. Heparinized blood (40 ml) will be taken at each of these time points and PBMC isolated. The following 8-12 marker panels will be run on a BD LSRFortessa (with appropriate FMO controls): 1) Treg/effector T cell activation panel: CD3, CD4, CD8, CD25, CD127, CD45RA, Ki67, FoxP3, HLA-DR, CTLA-4, PD-1, CD27; 2) Dendritic cell panel:

CD1c/BDCA-1, CD202/BDCA-2, CD141/BDCA-3, M-DC8 (Sulph-LacNac), CD14, CD11c, CD16, CD19, CD40, CD80, PD-L1; 3) Myeloid-derived suppressor cell panel: CD11b, CD14, CD33, CD3/19/56 (Lin), HLA-DR, CD15, CD16, PD-L1. By performing these analyses at the indicated time points, we will gain unique insight in the kinetics of T cell activation following SBRT and PD-1 blockade and pre-, on- and post-treatment immune effector/suppressor subset profiles that may show differences between the two treatment arms, as we previously showed in a trial of combined ipilimumab and Prostate GVAX immunotherapy (76-78).

7.1.2.11 Ultrasound endoscopy guided cytological lymph node aspiration for immunological cell composition (EBUS FACS)

Patients will undergo an EBUS-FNA of the ipsilateral and contralateral hilar and mediastinal lymph nodes within 2 weeks before and between week 2 and 3 after SBRT (see section 5.4).

7.1.3 Withdrawal/Discontinuation

When a subject discontinues/withdraws prior to trial completion, all applicable activities scheduled for the final trial visit should be performed at the time of discontinuation. Any adverse events which are present at the time of discontinuation/withdrawal should be followed in accordance with the safety requirements outlined in Section 7.2 - Assessing and Recording Adverse Events.

7.1.4 Visit Requirements

Visit requirements are outlined in Section 6.0 - Trial Flow Chart. Specific procedure-related details are provided above in Section 7.1 - Trial Procedures.

7.1.4.1 Screening

7.1.4.1.1 Screening Period

Visit requirements are outlined in Section 6.0 - Trial Flow Chart. Specific procedure-related details are provided above in Section 7.1 - Trial Procedures.

Potential subjects will be evaluated to determine that they fulfill the entry requirements as set forth in Section 5.1. Written consent must be obtained prior to performing any protocol specific procedure. Results of a test performed prior to the subject signing consent as part of routine clinical management are acceptable in lieu of a screening test if performed within the specified time frame. Screening procedures are to be completed within 30 days prior to the first dose of trial treatment except for the following:

- Laboratory tests are to be performed within 10 days prior to the first dose of trial treatment.
- Tumor imaging must be performed within 14 days prior to the first dose of trial treatment.

Subjects may be rescreened after initially failing to meet the inclusion/exclusion criteria. Results from assessments performed during the initial screening period are acceptable in lieu of repeating a screening test if performed within the specified time frame and the results meet the inclusion/exclusion criteria.

7.1.4.2 Treatment Period

Visit requirements are outlined in Section 6.0 - Trial Flow Chart. Specific procedure-related details are provided above in Section 7.1 - Trial Procedures.

7.1.4.3 Post-Treatment Visits

Visit requirements are outlined in Section 6.0 - Trial Flow Chart. Specific procedure-related details are provided above in Section 7.1 - Trial Procedures. Subjects will have post-treatment follow-up for experiencing disease progression, until death, withdrawing consent, becoming lost to follow-up or the start of new anti-neoplastic therapy.

7.1.5.3.1 Safety Follow-Up Visit

The mandatory Safety Follow-Up Visit should be conducted approximately 30 days after the last dose of trial treatment or before the initiation of a new anti-cancer treatment, whichever comes first. All AEs that occur prior to the Safety Follow-Up Visit should be recorded. Subjects with an AE of Grade > 1 will be followed until the resolution of the AE to Grade 0-1 or until the beginning of a new anti-neoplastic therapy, whichever occurs first.

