5.10 Subject Withdrawal/Discontinuation Criteria

Subjects may withdraw consent at any time for any reason or be dropped from the trial at the discretion of the investigator should any untoward effect occur. In addition, a subject may be withdrawn by the investigator or the PI if enrollment into the trial is inappropriate, the trial plan is violated, or for administrative and/or other safety reasons. Specific details regarding discontinuation or withdrawal are provided in Section 7.1.3.

A subject must be discontinued from the trial for any of the following reasons:

- The subject or legal representative (such as a parent or legal guardian) withdraws consent.
- Confirmed radiographic disease progression
- Unacceptable adverse experiences
- Intercurrent illness that prevents further administration of treatment
- Investigator's decision to withdraw the subject
- The subject has a confirmed positive serum pregnancy test
- Noncompliance with trial treatment or procedure requirements
- The subject is lost to follow-up
- Administrative reasons

The End of Treatment and Follow-up visit procedures are listed in Section 6 (Trial Flow Chart) and Section 7.1.4 (Visit Requirements). After the end of treatment, each subject will be followed for 30 days for adverse event monitoring. Subjects who discontinue for reasons other than progressive disease will have post-treatment follow-up for disease status until disease progression, initiating a non-study cancer treatment, withdrawing consent or becoming lost to follow-up.

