6.0 TRIAL FLOW CHART

6.1 Study Flow Chart

Trial period	Screening Phase	Imaging	Induction treatment phase	Surgery	Follow-up
Scheduling Window (Days)	-30 to -1	-14 to 0	From day 1 to day 56 (2 weeks after 2 nd pembrolizumab cycle)	From day 56 to day 70	From surgery to 6 months thereafter
Administrative Procedures					
Informed Consent	X				
Eligibility Criteria	X				
Demographics and Medical History	X				
Prior and Concomitant Medication Review	X				
PET Imaging					
⁸⁹ Zr-pembrolizumab		X ^a			
Clinical Procedures/Assessments					
Review Adverse Events	X		X ^b		
Full Physical Examination	X				
Directed Physical Examination	X		X ^b		X ^c
Vital Signs and Weight	X		X ^b		
ECOG Performance Status	X		X ^b		
12-lead ECG	X				
¹⁸ F-FDG PET-CT		X		X	
Laboratory Procedures/Assessments					
Pregnancy Test	X				
Complete Blood Count (CBC)	X	X ⁱ	X ^b		
Comprehensive Serum Chemistry Panel	X		X ^b		
Urinalysis	X				
T3, FT4 and TSH	X		X ^d		
Treatment					
SBRT			X		
Pembrolizumab			X ^a		
Surgery				X	
Efficacy Measurements					
Tumor Imaging (CT thorax +/- abdomen and MRI brain)		X	X ^e		X ^f
Tumor Tissue and Blood analysis					
Core tumor biopsy	X				
EBUS FACS		X	X ^g		
Surgical resection specimen				X	
Immunophenotyping		X ^h	X ^h	X ^h	X ^h

X^a: only for patients randomized to the SBRT + pembrolizumab arm; X^b: every cycle; every 6 weeks; X^c: if indicated; X^d: after 2nd pembrolizumab cycle; X^e: within 2 weeks of surgery; X^f: following resection every 3 months for the first 2 years and every 6 months for the 3 years thereafter; X^g:; X^g:between week 2 and 3 after SBRT; . X^h: see section 7.1.2.10 for timepoints; Xⁱ: 72 and 144 hours post-injection for patients undergoing ¹⁸F-FGD-PET-CT

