7.2 Assessing and Recording Adverse Events

An adverse event is defined as any untoward medical occurrence in a patient or clinical investigation subject administered a pharmaceutical product and which does not necessarily have to have a causal relationship with this treatment. An adverse event can therefore be any unfavorable and unintended sign (including an abnormal laboratory finding, for example), symptom, or disease temporally associated with the use of a medicinal product or protocol-specified procedure, whether or not considered related to the medicinal product or protocol-specified procedure. Any worsening (i.e., any clinically significant adverse change in frequency and/or intensity) of a preexisting condition that is temporally associated with the use of (⁸⁹Zr-)pembrolizumab, is also an adverse event.

Changes resulting from normal growth and development that do not vary significantly in frequency or severity from expected levels are not to be considered adverse events. Examples of this may include, but are not limited to, teething, typical crying in infants and children and onset of menses or menopause occurring at a physiologically appropriate time.

Adverse events may occur during the course of the use of (⁸⁹Zr-)pembrolizumab in clinical trials or within the follow-up period specified by the protocol, or prescribed in clinical practice, from overdose (whether accidental or intentional), from abuse and from withdrawal. Adverse events may also occur in screened subjects during any pre-allocation baseline period as a result of a protocol-specified intervention, including washout or discontinuation of usual therapy, diet, placebo treatment or a procedure.

Progression of the cancer under study is not considered an adverse event unless it is considered to be drug related by the investigator.

All adverse events will be recorded from the time the consent form is signed through 90 days following cessation of treatment or the initiation of new anti-cancer therapy, whichever is earlier and at each examination on the Adverse Event case report forms/worksheets. The reporting timeframe for adverse events meeting any serious criteria is described in section 7.2.3.1.

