7.2.3 Immediate Reporting of Adverse Events

7.2.3.1 Serious Adverse Events

A serious adverse event is any adverse event occurring at any dose or during any use of (^{89}Zr -)pembrolizumab that:

- Results in death;
- Is life threatening;

- Results in persistent or significant disability/incapacity;
- Results in or prolongs an existing inpatient hospitalization;
- Is a congenital anomaly/birth defect;
- Is a new cancer (that is not a condition of the study);
- Is associated with an overdose;
- Is another important medical event

Details regarding the above criteria can be found in Table 6.

Progression of the cancer under study is not considered an adverse event unless it results in hospitalization or death.

Any serious adverse event, or follow up to a serious adverse event, including death due to any cause other than progression of the cancer under study that occurs to any subject from the time the consent is signed through 90 days following cessation of treatment, or the initiation of new anti-cancer therapy, whichever is earlier, whether or not related to (⁸⁹Zr-)pembrolizumab, must be reported within 24 hours to the PI.

In the event of the occurrence of any clinical AE or abnormal laboratory test value that is serious or medically important during the course of the study or the post-treatment period, irrespective of the treatment received by the subject, the investigator is obliged to immediately inform the PI. The immediate report by the investigator to the PI shall be followed by detailed, written, reports using the SAE report form (for an “initial” SAE or for “follow-up” information on a previous SAE).

All SAEs will be reported by the PI through the web portal *ToetsingOnline* to the accredited METC that approved the protocol, within 15 days after the PI has first knowledge of the serious adverse reactions.

SAEs that result in death or are life threatening should be reported expedited. The expedited reporting will occur not later than 7 days after the responsible investigator has first knowledge of the adverse reaction. This is for a preliminary report with another 8 days for completion of the report.

Additionally, any serious adverse event, considered by an investigator who is a qualified physician to be related to (⁸⁹Zr-)pembrolizumab that is brought to the attention of the investigator at any time outside of the time period specified in the previous paragraph also must be reported immediately to the PI and Merck.

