7.2.3.3 Events of Clinical Interest

Selected non-serious and serious adverse events are also known as Events of Clinical Interest (ECI) and must be reported within 24 hours to the PI and within 2 working days to Merck Global Safety. (Attn: Worldwide Product Safety; [contact])

For the time period beginning when the consent form is signed until treatment allocation/randomization, any ECI, or follow up to an ECI, that occurs to any subject must be reported within 24 hours to the PI and within 2 working days to Merck Global Safety if it causes the subject to be excluded from the trial, or is the result of a protocol-specified intervention, including but not limited to washout or discontinuation of usual therapy, diet, placebo treatment or a procedure.

For the time period beginning at treatment allocation/randomization through 90 days following cessation of treatment, or 30 days following cessation of treatment if the subject initiates new anticancer therapy, whichever is earlier, any ECI, or follow up to an ECI, whether or not related to pembrolizumab, must be reported within 24 hours to the PI and within 24 hours to Merck Global Safety.

Events of clinical interest for this trial include:

1. an overdose of pembrolizumab, as defined in Section 7.2.1 - Definition of an Overdose for This Protocol and Reporting of Overdose, that is not associated with clinical symptoms or abnormal laboratory results.
2. an elevated AST or ALT lab value that is greater than or equal to 3X the upper limit of normal and an elevated total bilirubin lab value that is greater than or equal to 2X the upper limit of normal and, at the same time, an alkaline phosphatase lab value that is less than 2X the upper limit of normal, as determined by way of protocol-specified laboratory testing or unscheduled laboratory testing.*

*Note: These criteria are based upon available regulatory guidance documents. The purpose of the criteria is to specify a threshold of abnormal hepatic tests that may require an additional evaluation for an underlying etiology.

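### The flow chart marks no adverse-event review after surgery, and the recording period is 30 or 90 days from an undefined end of treatment, so postoperative safety cover depends on the reading

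*Combined protocol and SAP*

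**What the plan says.** **Scope of the safety aim.** Sections 2.1, 4.2.1 and 4.2.4 describe the primary safety aim as covering all three treatments, surgery included. The trial summary (section 1.0), section 3.1 and the decision rule in section 8.1 speak only of SBRT plus pembrolizumab. Section 4.2.4 itself goes on to name clinical signs of radiation pneumonitis as the safety measure, which agrees with section 8.1.

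**Scheduled review.** In the flow chart (section 6.1) the row "Review Adverse Events" is marked at screening and, per cycle, in the induction phase. Its Surgery and Follow-up cells are empty. Surgery is placed "From day 56 to day 70". No column exists for a safety visit.

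**Safety visit.** Section 7.1.5.3.1: "The mandatory Safety Follow-Up Visit should be conducted approximately 30 days after the last dose of trial treatment", or before new anti-cancer treatment if that comes first.

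**Length of the AE period.** Section 5.10: "After the end of treatment, each subject will be followed for 30 days for adverse event monitoring". Section 7.2 records all AEs "through 90 days following cessation of treatment or the initiation of new anti-cancer therapy, whichever is earlier and at each examination". Section 7.2.3.1 collects serious events "through 90 days following cessation of treatment, or the initiation of new anti-cancer therapy, whichever is earlier".

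**Meaning of treatment.** Section 5.6.2.2 uses the term for the infusion given each cycle. The flow chart lists surgery under its Treatment heading, and section 5.11 counts the three modalities together as one treatment. No section says which sense governs the AE period.

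**The concern.** Section 4.1.7 says that, to the authors' knowledge, no study has combined SBRT, immunotherapy and resection, and it expects no surgical complications beyond those of primary resection. Only postoperative data collected in the same way in both arms can test that expectation. As written, a site could hold its one mandatory safety visit before the operation, find no later AE review on the flow chart, and close AE monitoring at 30 or 90 days from whichever event it takes as the end of treatment. With 10 patients per arm, a few events missed or unevenly captured would alter the safety description.

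**Working it through.** **Reproducing the plan's dates.** Day 1 is the first fraction and, in the combination arm, the first infusion. Two 21-day cycles end on day 42, and 42 + 14 = day 56, the flow chart's end of induction. Eight and ten weeks are 8 × 7 = 56 and 10 × 7 = 70, the flow chart's surgery window.

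**Last dose or fraction.**
- SBRT arm (section 5.6.1.2, every second day): 3 fractions end on day 1 + 2×2 = 5; 5 fractions end on day 1 + 4×2 = 9. Assumption: this arm has no infusion, so the last fraction stands in for the last dose.
- Combination arm (section 5.6.2): dose 2 on day 1 + 21 = 22, or day 19–25 with the ±3-day tolerance in section 5.6.2.2.

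**Safety visit = last dose or fraction + 30.**
- SBRT arm: day 35 or 39. Days before surgery on day 56–70: 56 − 39 = 17 to 70 − 35 = 35.
- Combination arm: day 52 (49–55). Days before surgery: 56 − 52 = 4 to 70 − 52 = 18 (with tolerance, 56 − 55 = 1 to 70 − 49 = 21).
- If surgery is instead 8–10 weeks after each patient's own last dose or fraction (section 5.6.3): 56 − 30 = 26 to 70 − 30 = 40 days before surgery in both arms.
- If surgery is the anchor: 56 + 30 = day 86 to 70 + 30 = day 100, after surgery.
- If dose 2 is delayed to day 56 − 30 = 26 or later, the visit reaches day 56 or later.

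**Postoperative AE cover.** With the 90-day period counted from the last dose or fraction, the window ends on day 95 or 99 (SBRT arm) and day 112, or 109–115 with tolerance (combination arm).

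| Reading | SBRT arm | Combination arm |
|---|---|---|
| 90 days from last dose or fraction, flow-chart surgery | 95 − 70 = 25 to 99 − 56 = 43 | 112 − 70 = 42 to 112 − 56 = 56 (tolerance: 109 − 70 = 39 to 115 − 56 = 59) |
| 90 days from last dose or fraction, section 5.6.3 surgery | 90 − 70 = 20 to 90 − 56 = 34 | 20 to 34 |
| 90 days from surgery | 90 | 90 |
| 30 days (section 5.10) from last dose or fraction, flow-chart surgery, dose 2 not delayed | 0 (ends by day 39) | 0 (ends by day 55) |
| 30 days (section 5.10) from surgery | 30 | 30 |

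On section 5.6.3 timing the 30-day count from the last dose or fraction also ends before surgery (56 − 30 = 26 days at the least). The 90-day figures shorten for a patient who starts new anti-cancer therapy within the window.

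**The case against.** A reader might infer that postoperative AEs go unrecorded. The documents do not support that. Section 7.1.2.1 records adverse experiences throughout the study and allows extra assessments when indicated. Section 7.2 records AEs at each examination within its window. Section 7.1.5.3.1 follows AEs above Grade 1 until they resolve or new anti-neoplastic therapy begins. Section 7.2.3.1 requires immediate notice of events that are "serious or medically important during the course of the study or the post-treatment period", whatever treatment was received. All of this stands and narrows the point to scheduled capture of mainly non-serious events.

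A reader might also infer that the safety visit always precedes surgery. It does so only if the last dose excludes surgery, and only on an undelayed schedule. Section 5.6.2.2 favours that meaning; the flow chart's Treatment heading and section 5.11 leave the other open.

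The 0-day figure is the weakest of the readings. It rests on one sentence in the withdrawal section, whereas sections 7.1.2.1 and 7.1.3 refer to section 7.2, which gives 90 days. Nor is unequal cover between arms inevitable: it arises on flow-chart timing and disappears when surgery is timed from each patient's own last dose or fraction.

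The flow-chart footnotes are partly garbled. A six-weekly interval has no clear owner, so a fixed follow-up examination cannot be fully excluded. The empty AE cells themselves are unlikely to be an extraction fault, because other rows keep their marks in the Surgery or Follow-up columns.

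Finally, section 8.1 judges safety only on grade ≥3 pneumonitis. Such cases would usually be reportable as serious or medically important, so the effect on that rule is small. This stands too. What it leaves untouched is the wider safety aim in sections 2.1, 4.2.1 and 4.2.4.

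**Conclusion.** The point holds as an inconsistency worth correcting, not as an absence of safety data. The protocol states a primary safety aim that includes surgery, marks no AE review after surgery, and gives two AE periods without defining where either starts. Under the 90-day text, planned postoperative cover is 20–59 days from the last dose or fraction, or 90 days from surgery; under the 30-day text it is 0 or 30 days. On flow-chart timing with the last-dose or last-fraction anchor, cover is shorter in the SBRT arm (25–43 against 42–56 days); on section 5.6.3 timing it is 20–34 days in both. These figures assume an undelayed second dose, the last fraction as anchor in the SBRT arm, and no new anti-cancer therapy within the window.

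**What to change.** 1. State whether surgical toxicity is part of the primary safety endpoint, and align sections 1.0, 2.1, 3.1, 4.2.1, 4.2.4 and 8.1 with the answer.
2. Reconcile sections 5.10, 6.1, 7.1.5.3.1, 7.2 and 7.2.3.1 to one AE recording period, with one defined anchor that applies equally to both arms and covers the postoperative period. Say what treatment means for this purpose.
3. Mark AE review in the Surgery and Follow-up columns at contacts already planned: the blood draw one week after surgery and the 6-month blood draw (section 7.1.2.10), and the first 3-monthly CT (section 7.1.2.6). Repair the flow-chart footnotes at the same time.

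The cost is amendment wording plus about 20 patients × 3 contacts = 60 AE reviews, slightly more if subjects replaced under section 5.11 are also reviewed. The planned contacts are blood draws and scans, and section 7.2.4 requires a qualified physician to evaluate AEs, so each review takes investigator time. More routine postoperative events will appear in the tables and are best shown separately.
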